2. TRIAL DESIGN

2.1 OVERVIEW

Flow Chart: Study Overview

Eligibility

Adult undergoing a split skin graft harvest

- Between 18 and 90 years of age
- Not having a pacemaker or ICD
- Not pregnant
- Not mentally incapacitated
- No history of epilepsy or aneurysm
- No history of allergy to LA or TENS electrodes
- No history of undiagnosed skin/pain conditions
- Not taking part in other trials

Appropriate CONSENT process

RANDOMISE

(TENS/EMLA)
BP and pulse recording

Apply TENS/EMLA

Administer LA injection (30 minutes after TENS, 60 minutes after EMLA)
Record BP and Pulse before injection.

Complete Numeric pain rating scale and BP and Pulse chart

TENS-LA trial is a randomised control trial to assess the possible efficacy of Transcutaneous Electrical Nerve Stimulation (TENS) on eliminating or reducing the pain of local anaesthetic injection for minor surgical procedures. Comparison is done with a mixture of local anaesthetic cream (EMLA) which is used at times for the same purpose. Though local procedures are carried out in various parts of the body, this trial will be conducted specifically on patients undergoing a split skin graft harvest from the thigh. Patients who meet the eligibility criteria and are willing to participate will be randomised to receive either TENS or EMLA.

Eligible patients: Adult patients listed to have a split skin graft harvest under local anaesthesia will be assessed for eligibility for taking part in the trial.

2.2 SETTINGS

The study will be conducted at Leicester Royal Infirmary by the Department of Plastic Surgery.

2.3 SAMPLE SIZE

The study is designed to detect a difference of 3 units in pain scale between the 2 groups at 0.05 significance level and 90% power. We assume the standard deviation as 3 and the number of participants in each group has been calculated as 22. The total number of the patients including both arms of the trial will be 44.

2.4 ELIGIBILITY CRITERIA

Both interventions will be carried out in adult patients. For the purpose of standardisation and avoiding the variations from different sites in the body, and different surgical procedures, the site will be the thigh in both groups which is the donor site for a split skin graft.

Inclusion criteria:

Adult patients aged 18 to 90 years undergoing a split skin graft harvest under local anaesthesia

Exclusion criteria:

Patients below 18 and above 90 years of age

Patients with dementia or any other mental abnormalities who do not have the capacity to consent.

Pregnant ladies

Patients with pace maker or ICD

Patients with history of epilepsy or aneurysm
Patients with history of allergy to local anaesthetic or TENS electrodes
Patients with undiagnosed skin or pain conditions
Patient taking part in other studies

2.5 ETHICAL CONSIDERATIONS, INFORMATION GIVING AND WRITTEN INFORMED CONSENT

As outcome assessment involves a pain scale rating which has to be carried out by patient and requires that the patient be capable of providing this rating, the trial will not involve patients who are mentally incapacitated.

The investigator will explain to the patient that the trial is conducted to assess the effectiveness of TENS in alleviating the pain associated with local anaesthetic injection in comparison to EMLA and such trials have been conducted as research elsewhere and are safe. An information sheet will be provided and the patient is given the option to participate in the study. If they wish to be included, a written informed consent will then be taken. If the patient does not wish to enter the study, their choice will in no way affect their planned surgical treatment and post-operative care which will be carried out as per departmental standards.

2.6. REGULATORY REVIEW

Before any patients are enrolled, the Chief Investigator/Principal Investigator will ensure that appropriate approvals are in place. For any amendment to the study, the Chief Investigator in agreement with the Sponsor will submit information to the appropriate body in order for them to issue approval for the amendment.

2.7 RANDOMISATION

After obtaining informed consent patients will be randomised to two groups using codes generated by web-based randomisation system- Research Randomizer. This is a free resource for researchers. The website is http://www.randomizer.org
The numbers generated will be placed in separate sealed envelopes by the department secretary and made available to the investigators.

2.8 TRIAL INTERVENTION

On the day of procedure, either the Chief Investigator or Investigator will see the patient in the Theatre Arrivals area and have a full discussion on the details of the trial and will answer all their questions. Patients willing to take part and are within the inclusion criteria and does not have any of the exclusion criteria will be randomised to either the study group or the control group after obtaining informed consent.

The trial group will have the TENS to the area planned for injection for at least 30 minutes before injection of the local anaesthetic.

The control group will have EMLA 5% applied on the site planned for local anaesthetic injection and after a minimum period of 1 hour, will be removed and immediately injected with the same anaesthetic solution (this is already a procedure practiced by some of the surgeons).

Pain perception will be evaluated using two Numeric Pain Rating Scales in the study and control groups- one to assess the pain of needle penetration and the second to assess the pain of local infiltration. The Numeric pain scale is filled in by the doctor as indicated by the patient. Pulse rate and Blood Pressure monitoring will be carried out as an objective measurement of response to pain (these are routinely recorded when patient is in the theatre for a procedure). Patient involvement in the study ends at this point.

Analysis of the outcome will be done at the end of the trial period.

Description of device

The TENS unit comprises of an

- (1) Electric pulse generator which is battery-operated and programmable for pulse rate, width and intensity.
- (2) Lead wires connecting the unit to electrodes
- (3) Electrodes which consists of silicone rubber and adhesive to attach to skin surface.

Specifications of the unit to be used.

The device to be used in the trial is Neurotrac TENS Unit

Power supply : PP3 Alkaline battery, 9 volts

Pulse rate : 80Hz -100Hz

Pulse width : 50 - 300 microsecondsAmplitude : 0-80mA (500 Ohm load)

Type : Continous

Contraindications

1. In patients with pacemakers or implantable cardioverter-defibrillators (ICDs)¹⁴. This is of utmost significance for use in thoracic area as there will be interference with the electrical impulses generated except in fixed rate pacemakers.

- 2. Epileptic patients as there is a risk of triggering a seizure.
- 3. Patients with history of aneurysm. TENS stimulates peripheral blood flow and hence can be problematic in such cases.
- 4. Pregnant patients. There are no definitive side effects and some studies¹⁵ have demonstrated the effectiveness and safety of TENS use during pregnancy. But as such it has not been approved for use in pregnancy.
- 5. By patients with undiagnosed skin or pain conditions

2.9 ADVERSE EVENTS

EMLA Cream and TENS have a well-documented safety profile. The commonest side effect for TENS reported is allergic reaction (2-3%) to the electrodes, gel or the tapes used for fixing electrodes. Any adverse events/ reactions to either EMLA or TENS machine will be collected and reported in the Case Report Form. Due to the minimal risk presented, Serious Adverse Events will not be collected for this study.

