2.11 DATA COLLECTION AND MANAGEMENT

The trial will be conducted at Leicester Royal Infirmary and data collection done by investigators on site. Data on eligibility will be available in the case report form. Other data will include consent form, outcome assessment forms and data on adverse events/ reactions. Paper data will remain at the trial site itself in locked cabinet and will only be accessed by the investigators. For the purpose of analysis data will be transcribed to excel spreadsheet. Data will be used only in accordance with the data protection act and ethical considerations. Any data analysed or seen by other parties will be pseudo-anonymised by allocating a number to everyone.

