2.12 MONITORING

University Hospitals of Leicester NHS Trust, as Sponsor, operates a risk based monitoring and audit program to which the study will be subject. The trial will collect data on any adverse event/ reaction. All trial related documents will be kept for at least five years after completion of the trial.

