3.3 COLLABORATOR'S RESPONSIBILITIES

The responsibilities of the chief investigator will be detailed in advance of starting the trial and will include:

- Ensure all necessary approvals are in place prior to starting the trial
- Delegate responsibilities related to the trial only to suitably qualified and trained personnel
- Ensure that patients fulfilling eligibility criteria and considered for the trial
- Ensure patients are given adequate information regarding the trial and informed consent obtained
- Ensure that the documentation is up to date
- Ensure that all adverse effects related to the trial are promptly reported
- Ensure that the trial is conducted in accordance with the ICH GCP and fulfils local and national guidelines.
- Hold the responsibility for archiving the original trial documents for 5 years after end of trial

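### Section 2.9 both requires and rules out collection of a serious reaction to EMLA or TENS, and Section 2.12 does not resolve it

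*Protocol*

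**What the plan says.** Four places in the protocol bear on which harms are recorded.

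- **Section 2.9, collection:** "Any adverse events/ reactions to either EMLA or TENS machine will be collected and reported in the Case Report Form".
- **Section 2.9, the sentence that follows:** "Due to the minimal risk presented, Serious Adverse Events will not be collected for this study".
- **Section 2.12:** "The trial will collect data on any adverse event/ reaction".
- **Section 2.11, listing the trial data:** "Other data will include consent form, outcome assessment forms and data on adverse events/ reactions".

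A related duty is placed on the chief investigator in Section 3.3: "Ensure that all adverse effects related to the trial are promptly reported". Section 2.9 also gives the only reaction rate in the document: "The commonest side effect for TENS reported is allergic reaction (2-3%) to the electrodes, gel or the tapes used for fixing electrodes".

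**The concern.** The two consecutive sentences of Section 2.9 overlap. A serious reaction to EMLA or to the TENS device is a reaction to an intervention, so the first sentence calls for it to be recorded. It is also a serious adverse event, so the second says it is not collected. Site staff have no rule for choosing between them.

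The harms record is at stake. Followed literally, the last sentence keeps a mild skin reaction and drops a severe one. A final report showing no serious events could then not be interpreted, because a true absence would look the same as non-collection. That matters here because the introduction of the protocol puts TENS forward as a safe device for minor surgery should it prove effective.

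**Working it through.** **Comparing the rules.** The question is what each statement tells an investigator to do with a given event.

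| Event | 2.9, collection sentence | 2.9, last sentence | 2.12 |
|---|---|---|---|
| Non-serious reaction to EMLA or TENS | Record | Silent | Record |
| Serious reaction to EMLA or TENS | Record | Do not collect | Record |
| Serious event unrelated to either | Not covered | Do not collect | Record |

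The second row is a conflict within Section 2.9 itself and between 2.9 and 2.12. The third row is a conflict between 2.9 and 2.12, because the wording of 2.12 is not confined to related events. Section 2.11 lists adverse event data with no exclusion. Section 3.3 concerns prompt reporting of trial-related effects; it points towards capturing them but does not say what goes on the Case Report Form. No visible text reconciles these statements.

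**How many patients could be involved.** The number of serious events lost cannot be calculated, since no serious-event rate is given. A rough upper figure is possible for one type of reaction.

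Inputs:
- TENS group size 22, from Section 2.3: "the number of participants in each group has been calculated as 22". This reproduces: with a difference of 3, SD 3, two-sided 0.05 (sidedness assumed) and 90% power, n = 2 × (1.960 + 1.282)² × (3/3)² = 21.02, rounded up to 22 per group.
- Allergic reaction to electrodes, gel or tape, any severity: 2% to 3%, from Section 2.9. It is assumed that this rate applies to the trial's single short application and that patients are independent.

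Expected reactions = n × p:
- 22 × 0.02 = 0.44
- 22 × 0.03 = 0.66

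Probability of at least one = 1 − (1 − p)ⁿ:
- 1 − 0.98²² = 0.359
- 1 − 0.97²² = 0.488

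So there is a 36% to 49% chance of seeing at least one such reaction of any severity. Serious ones are an unstated fraction of these, so under the assumed rate the figures are an upper limit for serious reactions of this type. The limit is probably generous, because Section 2.4 excludes "Patients with history of allergy to local anaesthetic or TENS electrodes". No rate is given for EMLA or for any other TENS reaction, so neither can be sized.

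**The case against.** The strongest reply is that the two sentences can be read together. The collection sentence is about reactions to the interventions. The sentence on serious events gives minimal risk as its reason and may have been meant only to waive a general serious-event stream in surgical patients, or a separate reporting route. Sections 2.11, 2.12 and 3.3 all point towards collection, and one sentence stands against them. This may well be what was intended, but the text does not say so: it speaks of collection, not of reporting route, and it is not limited to unrelated events. Even on this reading, a waiver of unrelated serious events would still contradict Section 2.12.

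A second reply is that little can be lost. Under Section 2.8 a patient's involvement ends once the pain scales, pulse and blood pressure have been recorded at injection. Section 2.4 excludes the groups named as contraindicated. Even a complete record of no serious events in 22 patients would leave a one-sided 95% upper bound of 1 − 0.05^(1/22) = 12.7%. These points stand, and they limit the importance of the finding. They do not make opposite instructions consistent, and an exclusion based on history cannot catch a first reaction. A small trial that cannot rule out a moderate risk should still record any serious reaction that does occur.

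A third reply is that the 36% to 49% does not measure the disputed event. That is correct: it covers reactions of any severity and serves only as an upper limit under the stated assumption. The contradiction does not depend on it.

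**Conclusion.** The concern holds. Sections 2.9 and 2.12 give opposite instructions for a serious reaction to EMLA or TENS, and nothing in the document resolves them. This is an inconsistency in a rule the protocol does state, so it does not turn on detail that a statistical analysis plan might supply.

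The practical size is small: probably few patients, if any. The duty in Section 3.3 is a partial safeguard, since it may bring a serious related effect to light even where the form does not. The damage is confined to the harms record. The change should be made, but it does not threaten the trial's main result.

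The conclusion rests on the visible text alone. The Case Report Form (Appendix 3) is not shown and may already be fuller than Section 2.9 implies.

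**What to change.** Delete the last sentence of Section 2.9, or reword it to state exactly what is waived. Then bring Sections 2.9 and 2.12 into line, consistent with 2.11 and 3.3, so that each adverse event or reaction to EMLA or TENS is entered on the Case Report Form whether or not it is serious, with its seriousness marked. If the sponsor wishes to waive serious events unrelated to either intervention, Section 2.12 should carry the same limit or refer back to 2.9.

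The cost is a wording change to one sentence in 2.9 and, if any waiver is kept, to one in 2.12. If the form does not already record seriousness, one field is added. The sample size and the primary analysis do not change.

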2.10 OUTCOME ASSESSMENT

Pain perception will be evaluated using two Numeric Pain Rating Scales in the study and control groups. One scale will assess the pain caused by needle piercing the skin and the second will do so for the pain caused by infiltration of local anaesthetic agent.

Pulse rate and Blood Pressure monitoring will be carried out as an objective measurement of response to pain.

2.11 DATA COLLECTION AND MANAGEMENT

The trial will be conducted at Leicester Royal Infirmary and data collection done by investigators on site. Data on eligibility will be available in the case report form. Other data will include consent form, outcome assessment forms and data on adverse events/ reactions. Paper data will remain at the trial site itself in locked cabinet and will only be accessed by the investigators. For the purpose of analysis data will be transcribed to excel spreadsheet. Data will be used only in accordance with the data protection act and ethical considerations. Any data analysed or seen by other parties will be pseudo-anonymised by allocating a number to everyone.

2.12 MONITORING

University Hospitals of Leicester NHS Trust, as Sponsor, operates a risk based monitoring and audit program to which the study will be subject. The trial will collect data on any adverse event/ reaction. All trial related documents will be kept for at least five years after completion of the trial.

2.13 ANALYSIS

The analysis will assess the effectiveness of TENS in alleviating the pain of local anaesthetic injection with the differentiation of needle and infiltration pain and also compare the TENS with EMLA. It is expected that TENS will alleviate or bring about a significant reduction in the pain associated with injection of local anaesthetic and will be better or as effective as EMLA in this aspect. This is the hypothesis being examined in this trial.

Pain perception will be evaluated using two Numeric Pain Rating Scales in the study and control groups. Pulse rate and Blood Pressure monitoring will be carried out as an objective measurement of response to pain.

The tabulation of the results will be done by the research team after transcribing to an excel spreadsheet and the fully anonymised data will be analysed statistically by the biostatistician at The University of Leicester.

Summary statistics of 2 groups will be presented. Median score, lower and upper quartile and minimum and maximum scores will be given for each group. Two groups will be compared using Mann Whitney test.

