fibres (small fibres) inhibited. Thus, selective enhancement of input in large fibres shuts the Pain Gate band diminishes any ongoing pain³.

The alternative mechanism of pain relief by TENS is that it stimulates the release of endogenous opioids in the spinal cord. Low frequency and high frequency TENS function through activation of mu and delta opioid receptors respectively^{4,5}.

TENS was used by Wall and Sweet on patients experiencing pain, increasing the voltage till tingling was experienced in the area and resulted in relief of pain during the stimulation and for 30 minutes after.

The intensity or amplitude of TENS is directly related to the positive effect- a strong intensity (barely comfortable) provides significant analgesic effect.

A systematic review and meta -analysis on the effectiveness of TENS on post-operative analgesia by Bjordal et al⁸ concluded that there is significant reduction in analgesic consumption for post-operative pain when TENS is administered with a strong intensity at an adequate frequency in the area.

TENS was found to be a good alternative to local anaesthetic in children requiring restorative dental procedures in many studies^{9,10}.

TENS was found to be more effective than local anaesthetic gel prior to inferior alveolar block injection in children in reducing the pain of injection in a study by Choudhari et al¹¹ which confirmed the findings from a similar study earlier by Meechan et al¹².

TENS was found to be almost equally effective as 2% local anaesthetic injection during minor paediatric dental procedures and more comfortable and preferred by 93.3% of the patients over the local anaesthetic in a study by Dhindsa et al¹³.

Objectives

The primary aim of this study is to evaluate the possible effectiveness of TENS in reducing the pain associated with local anaesthetic injection and to compare it with the use of topical anaesthetic cream. The hypothesis is that TENS is effective in alleviating/reducing the pain of local anaesthetic injection and more or equally effective compared with local anaesthetic cream for this purpose.

Methods and design

The study is planned as a randomised control trial with 2 arms:

- 1- The control group will have a local anaesthetic cream EMLA (Eutectic Mixture of Local Anaesthetics) applied for a minimum period of 60 minutes before injection of local anaesthetic
- 2- The study group will have TENS applied for a minimum period of 30 minutes before injection of local anaesthetic

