Two electrodes will be placed - one proximal and the other distal to the area marked for harvest of skin graft on the thigh a distance of 10 cm.

Conventional treatment mode Programme 1 will be used with a rate of 80Hz -100Hz and pulse width of 200 micro seconds. The intensity will be gradually increased till patient experiences steady continuous stimulation but no muscle contraction. This is maintained for a period of 30 minutes after which the local anaesthetic injection is carried out.

Rationale

Though there have been several publications on the benefits of TENS as a local anaesthetic and also to reduce the pain of local anaesthetic injections, such a research is lacking in the surgical specialties. This trial would help to fill in this gap in evidence and help to make better evidence-based decisions.

If found to have a statistically significant benefit over the use of EMLA to alleviate the pain of local anaesthetic injection, TENS will be the way forward for minor operations for the purpose. The most dreaded part of the procedure for the patient is made more tolerable.

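### The declared hypothesis lets TENS be as effective as EMLA, but the protocol has only a test of difference and no margin, so a null result could be read as equality

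*Protocol*

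**What the plan says.** The comparison with EMLA is described in four places in the protocol, and they do not describe the same question.

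- **Objectives (section 1):** TENS is hypothesised to be "more or equally effective compared with local anaesthetic cream for this purpose".
- **Analysis (section 2.13):** TENS "will be better or as effective as EMLA in this aspect", followed by "This is the hypothesis being examined in this trial". The single inferential method is given as "Two groups will be compared using Mann Whitney test". The other planned output is descriptive and per group: median, quartiles, minimum and maximum.
- **Sample size (section 2.3):** the trial is designed to "detect a difference of 3 units in pain scale between the 2 groups at 0.05 significance level and 90% power", with an assumed SD of 3, giving 22 per group and 44 in total.
- **Rationale (section 1):** adoption of TENS is conditional: "If found to have a statistically significant benefit over the use of EMLA to alleviate the pain of local anaesthetic injection".

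The first two allow either superiority or equal effectiveness. The last two concern a difference only. The protocol states no margin and no confidence interval for the between-group difference.

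**The concern.** A Mann-Whitney test can reject the hypothesis of no difference but cannot establish it. Failure to reject may mean that the treatments are similar, or only that the trial was too small to separate them. When the hypothesis is that TENS is better or as good, both a significant result in favour of TENS and a non-significant result can be presented as supporting it. Only a significant result against TENS would clearly contradict it.

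What is at stake is the conclusion that the trial will publish on equal effectiveness. The superiority test is not affected, and the adoption statement in the Rationale is protected because it asks for a significant benefit.

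**Working it through.** **Inputs.** From section 2.3: difference 3, SD 3, alpha 0.05, power 90%, 22 per arm. Sidedness is not stated. From section 2.13: Mann-Whitney test. The SDs of 2 and 2.5, all margins, and the true deficits of 1, 1.5 and 2 points are illustrative assumptions, because the protocol gives none.

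**1. The protocol's own figure.** Two-sided normal approximation: n per arm = 2 × (1.960 + 1.282)² × (3/3)² = 21.01, rounded up to 22. By the two-sample t-test, n = 22.02 per arm, and power at 22 is 0.900. A one-sided calculation would give 18. So 22 reproduces as a two-sided sample size for a difference. The calculation is correct, but it serves only the superiority question.

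**2. Precision at 22 per arm.** SE = SD × √(2/22). At SD 3, SE = 0.905, and the 95% half-width is t(0.975, 42 df) × SE = 2.018 × 0.905 = 1.83 points. At SD 2.5 it is 1.52, and at SD 2 it is 1.22.

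**3. How often a truly inferior TENS gives a non-significant result.** Mann-Whitney test, two-sided 0.05, normally distributed scores, 40,000 simulated trials per cell:

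| TENS truly worse by | SD 3 | SD 2.5 | SD 2 |
|---|---|---|---|
| 1 point | 0.819 | 0.760 | 0.650 |
| 1.5 points | 0.653 | 0.526 | 0.344 |
| 2 points | 0.443 | 0.286 | 0.116 |
| 3 points | 0.116 | 0.035 | 0.003 |

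The t-test approximation at SD 3 gives 0.81, 0.63 and 0.42 for the first three rows. Rounding the scores and bounding them to 0–10, with an assumed control mean of 4, gives 0.820, 0.658, 0.449 and 0.125 at SD 3.

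**4. How often truly equal arms would allow a non-inferiority conclusion.** This is the probability that the 95% CI excludes TENS being worse by the margin: P(T > 2.018), with T noncentral t on 42 df and noncentrality margin/SE. For example, at SD 3 and margin 1.5 the noncentrality is 1.5/0.905 = 1.66.

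| Margin | SD 3 | SD 2.5 | SD 2 |
|---|---|---|---|
| 1 point | 0.190 | 0.253 | 0.367 |
| 1.5 points | 0.367 | 0.494 | 0.681 |
| 2 points | 0.579 | 0.736 | 0.900 |
| 3 points | 0.900 | 0.973 | 0.998 |

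Power of 90% is reached at a margin of about 3.0 points (SD 3), 2.5 (SD 2.5) or 2.0 (SD 2), that is, one SD in each case. A looser one-sided 0.05 test at SD 3 (normal approximation) gives 0.295, 0.505, 0.714 and 0.953 for the four margins.

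**5. Size needed for a narrower margin at 90% power, true difference zero.** At SD 3: 48.3 per arm for 2 points and 85.0 for 1.5 points, so about 49 and 86. At SD 2: 22.0 and 38.3, so about 22–23 and 39.

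**The case against.** The strongest reply is that the harm is conjectural. The protocol nowhere says that a non-significant result will be reported as equality, and its one stated consequence requires a significant benefit over EMLA. Reporting rules and the display of a confidence interval are commonly left to a statistical analysis plan. This is right about reporting detail, and silence on reporting is not in itself the fault. What stands is a mismatch inside the protocol: it fixes the hypothesis, the test and the sample size itself, and they do not fit together. A margin also drives the sample size, so a later analysis plan could not make 22 per arm adequate for a narrow one.

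A second reply is that the limb is not untestable in principle, since 44 patients give 90% non-inferiority power at 3 points with SD 3, or at 2 points with SD 2. That is correct. The limb is untestable under the plan as written, because no margin or rule is stated. At the protocol's own SD, the adequately powered margin would equal the whole difference the trial was designed to detect.

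Third, most of the figures rest on assumed deficits, margins and SDs. Precision and non-inferiority power are computed on means, although the planned test is rank-based. In the bounded check, rounding and truncation also reduce the nominal SD of 3 and the 3-point shift to about 2.7 each. The numbers are therefore indicative, but the direction does not change.

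Finally, equal effectiveness is one alternative within the EMLA comparison. The hypothesis also says that TENS itself reduces injection pain, and that part is outside this point.

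**Conclusion.** The concern holds and should be fixed. The protocol declares a hypothesis with an equal-effectiveness alternative for which it provides no margin, no decision rule and no suitable analysis, and it sizes the trial for a different question. At the protocol's SD of 3, a TENS arm truly 1 to 1.5 points worse would give a non-significant result in roughly 82% to 65% of trials. With truly equal arms, a disadvantage of that size would be excluded in only 19% to 37%. If the SD were 2, the corresponding figures would be 65% to 34% and 37% to 68%, so the problem is smaller but still present. These figures assume 22 evaluable patients per arm, approximately normal scores and a two-sided 5% level. The sample size calculation, the superiority test and the adoption criterion are unaffected.

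**What to change.** Reconcile the Objectives and section 2.13 with section 2.3 and the Rationale, in one of two ways.

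- **Preferred: superiority only.** Restrict the confirmatory hypothesis to TENS being superior to EMLA, and add to section 2.13: *A non-significant result will be reported as inconclusive and not as evidence that TENS is as effective as EMLA.* It would help to report the Hodges-Lehmann difference (TENS minus EMLA) with its 95% confidence interval beside the Mann-Whitney p-value.
- **If the equal-effectiveness claim is kept:** allow it only when that interval excludes TENS being worse by a margin that is justified and fixed before any data are seen. State the power that 22 per arm gives for that margin.

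The first option changes wording only and needs no extra patients. It does need an amendment through the approval route in section 2.6, and the sponsor gives up an equal-effectiveness claim after a null result. The second option may require a larger trial: at SD 3 and 90% power, about 49 per arm for a 2-point margin or 86 for 1.5 points; at SD 2, about 22–23 or 39. Which aim is intended is for the sponsor to decide; the superiority option matches the existing design.
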